7. PRIMARY STATISTICAL ANALYSES

7.1. Efficacy Analyses

7.1.1. Overview of Planned Efficacy Analyses

The primary efficacy analyses will be based on the FA population, unless otherwise specified.

Table 3 provides an overview of the planned efficacy analyses, with full details of data displays being presented in [Appendix 14: List of Data Displays](#).

Table 3 Overview of Planned Efficacy Analyses

	Absolute							Change from Baseline						
	Stats Analysis			Summary		Individual		Stats Analysis			Summary		Individual	
	T	F	L	T	F	F	L	T	F	L	T	F	F	L
HbA _{1c}	Y			Y	Y		Y	Y	Y		Y	Y		Y

NOTES :

- T = Table, F = Figure, L = Listing, Y = Yes display generated.
- Stats Analysis = Represents TFL related to any formal statistical analyses (i.e. modelling) conducted.
- Summary = Represents TFL related to any summaries (i.e. descriptive statistics) of the observed raw data.
- Individual = Represents FL related to any displays of individual subject observed raw data.

Following review of the data, additional analyses may be conducted to further support the evaluation and interpretation of the data.

7.1.1.1. Primary Analysis on Primary Efficacy Endpoint

The primary efficacy endpoint is the change from Baseline in HbA_{1c} at Week 26. The primary analysis of the primary efficacy endpoint will be conducted using a mixed-effect model with repeated measures (MMRM) in the FA population using all available data from analysis visits. Missing data will not be imputed.

The model will include HbA_{1c} change from Baseline as the dependent variable; treatment, region (defined in [Appendix 8: Multicenter Studies and Definition of Geographic Region for Statistical Analysis](#)), age category, current metformin use, visit week, treatment-by-week interaction, and baseline HbA_{1c}-by-week interaction as fixed effects; baseline HbA_{1c} as a continuous covariate; and subject as a random effect (Model 1). Treatment effects estimates (and associated hypothesis tests) of albiglutide will be evaluated within this MMRM model as least squares means contrasts relative to insulin lispro. An unstructured covariance matrix will be used for the MMRM analysis, unless the model does not converge, in which case the covariance matrix will be decided upon model convergence status and the Akaike information criterion (AIC). The MIXED procedure in SAS will be used to implement the MMRM analysis. The least squares means (and standard errors) of HbA_{1c} at each study visit and least squares means (and standard errors) of change from Baseline in HbA_{1c} at each postbaseline study visit will be presented. The least squares mean and the associated 1-sided 97.5% confidence interval of the treatment difference in change from Baseline in HbA_{1c} at each postbaseline study visit will be reported. In addition, the observed HbA_{1c} and change from Baseline HbA_{1c}

will be summarized descriptively. The least squares means (and standard errors) of change from Baseline HbA_{1c} will be plotted by treatment group.

The null hypothesis will be tested based on the 1-sided 97.5% confidence interval of the least squares mean of the treatment difference at Week 26 estimated from the MMRM model. If the upper bound of the confidence interval is less than or equal to 0.3%, non-inferiority will be concluded. If non-inferiority is established, key secondary endpoints will be tested as described in Appendix 11.10.

7.1.1.2. Supportive Analyses on Primary Efficacy Endpoint

The MMRM analysis above assumes that there are no qualitative interactions of treatment with the other terms in the model. For the primary endpoint only, the treatment-by-baseline HbA_{1c}, treatment-by-region, treatment-by-age category, and treatment-by-current metformin use interactions will be investigated individually at a significance level of 0.10. Absence of a significant treatment-by-variable qualitative interaction at the 0.10 level will be interpreted as supportive of the use of the main-effects model to evaluate the treatment efficacy hypotheses. When examining the interaction between the continuous variable HbA_{1c} and treatment, the baseline HbA_{1c} category will be used.

The primary endpoint will also be analyzed using Model 1 in the PP population as supportive analysis.

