8.3.3. Treatment Comparisons

8.3.3.1. Primary Comparisons of Interest

The primary endpoint is the change from Baseline in HbA_{1c} at Week 26. The primary analysis of the primary endpoint will be conducted using a mixed-effect model with repeated measures (MMRM) in the FA Population. The MMRM will only include nonmissing observations without imputation.

The model will include HbA_{1c} change from Baseline at all postbaseline visits as dependent variables; treatment, region, age category, current use of metformin, visit week, treatment-by-week interaction, and baseline HbA_{1c}-by-week interaction as fixed effects; baseline HbA_{1c} as a continuous covariate; and subject as a random effect. Treatment effects estimates (and associated hypothesis tests) of albiglutide will be evaluated within this MMRM model as least squares means contrasts relative to insulin lispro. An unstructured covariance matrix will be used for the MMRM analysis, unless the model does not converge, in which case the covariance matrix will be decided upon model convergence status and the Akaike information criterion.

The generalizability of the treatment effect will be evaluated within a supportive analysis of covariance (ANCOVA) model that adds terms for treatment-by-variable interaction. The variables to be interacted with treatment include baseline HbA_{1c}, region, age category, and current use of metformin. Absence of a significant treatment-by-variable qualitative interaction at the 0.10 level will be interpreted as supportive of the use of the main-effects model to evaluate the treatment efficacy hypotheses.

The primary endpoint will also be analyzed using the same MMRM model in the PP Population as supportive analysis.

Special attention will be paid to the handling of missing data in statistical analysis. The method for the primary analysis, MMRM, assumes missing at random. The sensitivity of the results of analysis to the method of handling missing values will be investigated, especially if the number of missing values is substantial or if the characteristics of missing values differ between treatment groups. Further details of the sensitivity analysis,

including imputation methods and assumptions about the missing data, are described in Section 8.3.5.1.

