7.1.2. Planned Efficacy Statistical Analyses

Primary Statistical Analyses
Endpoint(s)

 Change from Baseline in HbA_{1c} at Week 26
Model Specification

 Change from Baseline in HbA_{1c} = Baseline HbA_{1c} + Treatment + Region + Age Category + Current Use of Metformin + Visit Week + Treatment-by-Visit Interaction + Baseline HbA_{1c}-by-Visit Week Interaction (Model 1)
Model Checking & Diagnostics

 Refer to Appendix 11: Model Checking and Diagnostics for Statistical Analyses
Model Results Presentation

 The least squares mean of the treatment difference at Week 26 estimated from the MMRM model and its 1-sided 97.5% confidence interval Descriptive statistics for the observed HbA_{1c} and change from Baseline HbA_{1c} Plot of the least squares means (and standard errors) of change from Baseline HbA_{1c} by treatment group Refer to Appendix 14: List of Data Displays
Supportive Statistical Analysis

 The generalizability of the treatment effect will be evaluated within a supportive MMRM model that adds terms for treatment-by-variable interaction. The variables include baseline HbA_{1c}, region, age category, and current use of metformin. The primary endpoint will also be analyzed using Model 1 above in the Per-Protocol Population
Model Specification

 Change from Baseline in HbA_{1c} = Baseline HbA_{1c} + Treatment + Region + Age Category + Current Use of Metformin + Visit Week + Treatment-by-Visit Interaction + Baseline HbA_{1c}-by-Visit Week Interaction + Treatment-by-Variable + Visit Week-by-Variable + Treatment-by-Visit Week-by-Variable. Refer to Appendix 11: Model Checking and Diagnostics for Statistical Analyses for SAS code
By-Subgroup Statistical Analysis

 The subgroup analyses will be performed using MMRM models. The subgroups include baseline HbA_{1c} category, gender, race, ethnicity, age category, baseline BMI category, region, duration of diabetes category and current use of metformin. Refer to Appendix 9: Examination of Covariates, Subgroups & Other Strata.
Model Specification

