8.1.2. Key Secondary Efficacy Endpoints

8.1.2.1. Proportion of Subjects Who Do Not Meet Prespecified Criteria for Severe, Persistent Hyperglycemia through Week 26

For this key secondary endpoint, subjects who do not meet prespecified criteria for severe, persistent hyperglycemia through Week 26 will be defined operationally as those subjects treated with once-weekly albiglutide that are able to replace prandial insulin without lispro re-introduction through Week 26. Note: For lispro re-introduction through Week 26 the time window is defined up to Week 25.

Proportion of subjects that are able to discontinue insulin lispro at Week 4 and do not meet prespecified criteria for severe, persistent hyperglycemia through Week 26 will be summarized descriptively for all the Albiglutide + Insulin Glargine arm subjects and for

subgroups of baseline HbA_{1c} category (<8.0%, ≥8.0%), region, (<65 years versus ≥65 years), current use of metformin (Yes, No) in the FA population. The 95% confidence interval of the proportions of subjects will be provided.

The insulin lispro that was re-introduced to albiglutide subjects will be characterized. Summary statistics for the number of injections, total dose, and time-to-re-introduction will be presented.

Additional exploratory analyses to identify potential risk factors for lispro re-introduction will be investigated. Potential risk factors include: baseline HbA_{1c}, baseline HbA_{1c} category, age, age category, metformin-use, duration of diabetes, weight, BMI, BMI category, time in insulin (at baseline), baseline HbA_{1c}, and total insulin dose at baseline. Time in insulin (at baseline) is defined as the earliest start date of prior insulin medications taken minus the date of first date of randomized study medication, plus 1.

8.1.2.2. Percentages of Subjects with Severe or Documented Symptomatic Hypoglycemia through Week 26

The percentage of subjects with severe or documented symptomatic hypoglycemia will be summarized descriptively by treatment and analyzed using a Cochran-Mantel-Haenszel (CMH) test, stratified by baseline HbA_{1c} category, region, age category (<65 years versus ≥65 years), current use of metformin (Yes, No) in the FA population.

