11.11. Appendix 11: Model Checking and Diagnostics for Statistical Analyses

11.11.1. Model Checking and Diagnostics for Statistical Analyses

1. Example SAS code for the primary efficacy analysis of the primary endpoint (Model 1)

```
ODS OUTPUT LSMeans= OUTLIBNAME.LSMeans SLICES= OUTLIBNAME.Diffs;
PROC MIXED DATA= INDATA;
  CLASS USUBJID TRT01PN REGION METFORMIN AGEGR1 AVISITN;
  MODEL CHG = BASE TRT01PN REGION METFORMIN AGEGR1 AVISITN
    TRT01PN*AVISITN BASE*AVISITN /DDFM =KR ;
  REPEATED AVISITN/SUB=USUBJID TYPE=UN;
  LSMEANS TRT01PN*AVISITN/SLICE=AVISITN CL DIFF;
  ESTIMATE 'Treatment difference at Week 26'
    TRT01PN 1 -1
    TRT01PN*AVISITN 0 0 0 0 1
                  0 0 0 0 -1 /CL ;
RUN;
```

2. Example SAS code for the supportive analysis – interaction terms- of the primary endpoint

For HbA1c (Baseline HbA1c category: HBGR1):

```
ODS OUTPUT LSMeans= OUTLIBNAME.LSMeans SLICES= OUTLIBNAME.Diffs;
PROC MIXED DATA= INDATA;
  CLASS USUBJID TRT01PN REGION METFORMIN AGEGR1 AVISITN HBGR1;
  MODEL CHG = HBGR1 TRT01PN REGION METFORMIN AGEGR1 AVISITN
    TRT01PN*AVISITN HBGR1*AVISITN TRT01PN*HBGR1
    TRT01PN*HBGR1*AVISITN /DDFM =KR ;
  REPEATED AVISITN/SUB=USUBJID TYPE=UN;
  LSMEANS TRT01PN*HBGR1*AVISITN/SLICE=AVISITN CL DIFF;

  ESTIMATE 'Treatment difference at Week 26 for Baseline HbA1c
  Category < 8.0%'
    TRT01PN 1 -1
    TRT01PN*AVISITN 0 0 0 0 1 0 0 0 0 -1
    TRT01PN*HBGR1*AVISITN 0 0 0 0 0 0 0 0 1 0
                          0 0 0 0 0 0 0 0 -1 0 /CL ;
RUN;
```

(or use the following statement to replace the 'LSMEANS' AND 'ESTIMATE' statements above:
SLICE HBR1*TRT01PN*AVISITN/SLICEBY(AVISITN='26') DIFF; and ODS table SLICETESTS to obtain p-value for the interaction at Week 26 (AVISITN=26).

For Age category, Metformin use or Region:

```
ODS OUTPUT LSMeans= OUTLIBNAME.LSMeans SLICES= OUTLIBNAME.Diffs;
PROC MIXED DATA= INDATA;
  CLASS USUBJID TRT01PN REGION METFORMIN AGEGR1 AVISITN;
  MODEL CHG = BASE TRT01PN REGION METFORMIN AGEGR1 AVISITN
    TRT01PN*AVISITN BASE*AVISITN TRT01PN*AGEGR1
    AVISITN*AGEGR1 TRT01PN*AGEGR1*AVISITN /DDFM =KR ;
  REPEATED AVISITN/SUB=USUBJID TYPE=UN;
  LSMEANS TRT01PN*AGEGR1*AVISITN /SLICE=AVISITN CL DIFF;

  ESTIMATE 'Treatment difference at Week 26 for Age category < 65'
    TRT01PN 1 -1
    TRT01PN*AVISITN      0 0 0 0 1 0 0 0 0 -1
    TRT01PN*AGEGR1*AVISITN 0 0 0 0 1 0 0 0 0 0
    0 0 0 0 -1 0 0 0 0 0 /CL ;
```

RUN;

Note: The contrasts may need to be adjusted for a different factor.

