5. Example SAS code for analysis on FPG change from baseline by baseline FPG tertiles

```
ODS OUTPUT LSMeans= OUTLIBNAME.LSMeans SLICES= OUTLIBNAME.Diffs;
PROC MIXED DATA= INDATA;
  CLASS USUBJID TRT01PN REGION METFORMIN AGEGR1 HBGR1 FPG_TTL
    AVISITN;
  MODEL CHG= FPG_TTL HBGR1 TRT01PN REGION METFORMIN AGEGR1
    AVISITN TRT01PN*AVISITN TRT01PN*FPG_TTL
    FPG_TTL*AVISITN TRT01PN*FPG_TTL*AVISITN /DDFM =KR;
  REPEATED AVISITN/SUB=USUBJID TYPE=UN;
  LSMEANS TRT01PN*FPG_TTL*AVISITN/SLICE=AVISITN CL DIFF;
  ESTIMATE 'Treatment difference at Week 26 for 1st Baseline FPG
  Tertile'
    TRT01PN -1 1
    TRT01PN*AVISITN      0 0 0 0 1 0 0 0 0 -1
```

```
TRT01PN*FPG_TTL*AVISITN 0 0 0 0 1 0 0 0 0 0  
0 0 0 0 0 0 0 0 0 0 -1  
0 0 0 0 0 0 0 0 0 0 /CL ;  
RUN;
```

5. Example SAS code for analysis on exposure-adjusted event rate with Poisson regression model

```
ODS OUTPUT LSMeans= Lsmeans Diffs=Diffs;  
proc genmod data=INDATA;  
  class USUBJID TRT01AN MCRIT2ML HBGR1 AGEGR1 METFMN CTRYGR1;  
  model NUMEVT1=TRT01AN MCRIT2ML HBGR1 AGEGR1 METFMN CTRYGR1/  
d=poisson offset=PYOFFSET;  
  repeated SUBJECT=USUBJID /corrw covb type=exch;  
  LSMEANS TRT01AN/ EXP ILINK E CL DIFF;  
run;
```

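### The treatment-by-baseline-HbA1c check uses only a <8% / ≥8% split, and example code for three supportive or exploratory models drops the continuous baseline

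*SAP*

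**What the plan says.** **The interaction check.** Protocol 8.3.3.1 puts baseline HbA1c in the primary model as a continuous covariate. For the supportive check it states: "The variables to be interacted with treatment include baseline" HbA1c, along with region, age category and metformin use. No category is mentioned. SAP 7.1.1.2 says that these "interactions will be investigated individually at a significance level of 0.10", and that finding no significant qualitative interaction at that level supports the main-effects model. Its rule beginning "When examining the interaction between the continuous variable" then substitutes the baseline HbA1c category. The cut appears in SAP 8.1.2.1 as "category (<8.0%, ≥8.0%), region", and again in SAP 11.9.2. The table of changes in SAP 2.1 lists only the insulin-dose definition.

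**The written models.** SAP 7.1.2 says: "The generalizability of the treatment effect will be evaluated within a supportive MMRM model that adds terms for treatment-by-variable interaction". Both the supportive and the by-subgroup formulas there keep baseline HbA1c and its interaction with visit.

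**The example code (SAP 11.11.1).**
- Primary model, and the age/metformin/region interaction models: "MODEL CHG = BASE TRT01PN REGION METFORMIN AGEGR1 AVISITN", with `BASE*AVISITN`.
- HbA1c interaction model: "MODEL CHG = HBGR1 TRT01PN REGION METFORMIN AGEGR1 AVISITN". `HBGR1` terms take the place of `BASE` and `BASE*AVISITN`. The baseline-HbA1c subgroup model does the same.
- FPG change by FPG tertile: "MODEL CHG= FPG_TTL HBGR1 TRT01PN REGION METFORMIN AGEGR1", with no continuous baseline FPG. SAP 8.2.5 refers to this code for its model specification. Protocol 8.3.3.2 says that an MMRM for a non-HbA1c endpoint takes that endpoint's own baseline as a covariate.

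**The concern.** The plan gives a null interaction result a job: it is read as reassurance that one overall treatment effect is enough. A less powerful check makes that reassurance easier to obtain. Baseline HbA1c is an obvious candidate modifier, since randomized subjects must have a qualifying HbA1c of 7.0–9.0% (Protocol 4.4). Under the planning difference of 0.0, a linear interaction of 0.3 per 1% HbA1c that crosses zero at 8% means a treatment difference of 0.3 in one direction at 7% and 0.3 in the other at 9%. Each end is then as far from zero as the whole 0.3% margin. No planned analysis tests treatment against continuous baseline HbA1c, so a graded pattern of this kind would be seen only through the two-level split.

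Dropping the continuous baseline from the code is a separate matter. Text and code disagree about the model, and baseline variation within a category or tertile is left in the residual.

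**Working it through.** **1. The plan's own figure.** Inputs from Protocol 8.2.1 and SAP Appendix 12: margin 0.3, SD 1.2, true difference 0, one-sided 0.025, 90% power. Then n = 2 × 1.2² × (1.960 + 1.282)² / 0.3² = 336.2, so 337 per arm, and 337 / 0.85 = 396.5, so 397 randomized per arm. This reproduces the plan. The documents give no power for the interaction check.

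**2. Information kept by the split.** For a linear interaction, the share kept is the squared correlation between baseline and the indicator of HbA1c ≥8.0%: r² = p(1 − p)(m₁ − m₀)² / Var(x), where p is the share at or above 8% and m₁, m₀ are the two category means. The baseline distribution is not in the documents, so these are assumed cases:
- Uniform on 7–9: 0.5 × 0.5 × 1² / (1/3) = 0.75, a loss of 25%.
- Normal centred at 8.0, truncated to 7–9, parent SD 1.2 down to 0.4: loss 27% to 35%.
- Parent mean 7.8–8.2, same SD range: loss 27–39%.
- Values clustered low (parent mean 7.5–7.6, SD 0.4–0.5, only 12–24% at or above 8%): loss 40–56%.

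The analysis baseline is the last value before first dose, which may differ from the qualifying Week -1 value. Adding noise of SD 0.2 to the cases centred at 8.0 gives a loss of 29–35%.

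**3. Power.** N = 2 × 337 = 674, SD 1.2, level 0.10 taken as two-sided (critical value 1.645). For slope g per 1% HbA1c, z = g × SDₓ × √(N/4) / 1.2; with the split, z is multiplied by √r². Take SDₓ = 0.48 and r² = 0.69, which fit a truncated normal with parent mean 7.9–8.0 and SD 0.6. At g = 0.3, z = 0.3 × 0.48 × √168.5 / 1.2 = 1.56 continuous and 1.29 split.

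| Assumed baseline | Slope | Continuous | Split |
|---|---|---|---|
| Truncated normal | 0.3 | 47% | 36% |
| Truncated normal | 0.5 | 83% | 70% |
| Uniform | 0.3 | 59% | 49% |
| Uniform | 0.5 | 93% | 86% |

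A 3,000-run simulation (single-visit ANCOVA, parent mean 7.8, SD 0.6) gave 45% versus 36% at 0.3 and 81% versus 67% at 0.5. Rejection rates at slope 0 were 9–10%.

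**4. What dropping `BASE` adds.** With an assumed slope b of change on baseline, residual variance is 1.44 − b²SDₓ² with `BASE` and 1.44 − b²SDₓ²r² without it. At b = −0.5, SDₓ = 0.48 and r² = 0.69 these are 1.382 and 1.400, a ratio of 1.013, so information kept falls from 69% to 68%. Over b = −0.3 to −0.7 it falls from 75% to 73–75% (uniform) and from 69% to 67–69% (truncated normal): 0–2 points. In the simulation, restoring `BASE` beside the category moved power only from 35.7% to 36.1% at slope 0.3, and from 66.5% to 67.1% at 0.5.

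**5. FPG by tertile.** For a normal variable, 0.207 of the variance lies within tertiles. Assume baseline SD 3 mmol/L, slope 0.5–0.9 and residual SD 2.5–3.0, none of which is in the documents. Within-tertile variance is 0.207 × 9 = 1.863. SE inflation is √(1 + 0.5² × 1.863 / 3.0²) = 1.03 at the low end and √(1 + 0.9² × 1.863 / 2.5²) = 1.11 at the high end.

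**The case against.** The strongest reply is that the check concerns a qualitative interaction, one where the effect changes direction. Categories suit that question, and the SAP's reference list includes a paper on testing qualitative interactions across patient subsets. A slope alone does not show a reversal. This stands as a reason to keep the two category estimates. It does not justify using the category alone: SAP 7.1.1.2 does not invoke that method, and the code points to an ordinary interaction p-value, which is no more a test of direction than a slope is.

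The split is also stated openly and uses the same 8.0% cut as the randomization stratum, although that stratum is defined on screening HbA1c. If the effect really stepped at 8%, the split would lose nothing. Both points are fair. At a slope of 0.3 even the continuous test has under 50% power in the truncated-normal case, so non-significance is weak evidence either way.

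The code is labelled as an example and the written HbA1c models keep the baseline, so the omission there is a mismatch to reconcile. For FPG, the text of SAP 8.2.5 speaks of adding the tertile, and the secondary FPG analysis keeps continuous baseline. The protocol's covariate sentence sits among the secondary endpoints, though that paragraph also covers mean daily SMBG glucose, which is exploratory. The FPG tertile analysis is exploratory, with no multiplicity control.

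A reader might infer that the missing `BASE` causes the information loss. It does not: nearly all of it comes from the split. Chance imbalance within an HbA1c category is also small. With values uniform within a 1-point category (SD 0.29), about 168 per arm per category and a slope of 0.5, its standard error is 0.5 × 0.29 × √(2/168) = 0.016% HbA1c.

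**Conclusion.** The point holds as a precision and consistency issue in supportive and exploratory analyses. The switch from continuous baseline to category departs from Protocol 8.3.3.1 and is not recorded in SAP 2.1. It costs about 25–35% of the information on a linear interaction when baseline is spread over 7–9% and roughly centred on 8%, and more if few subjects reach 8%. That is about 10–13 percentage points of power at slopes of 0.3 to 0.5 in the truncated-normal case, and 7–10 in the uniform case. These figures rest on an assumed baseline distribution and on linearity.

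The omission of `BASE` and `BASE*AVISITN` contradicts SAP 7.1.2 but costs only 0–2 points. The omission of baseline FPG departs from Protocol 8.3.3.2 and inflates the SE by about 3–11% under assumed SDs and slopes.

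A reader might go further and take the non-inferiority test to be weakened. The documents do not support that: the primary MMRM keeps continuous baseline HbA1c and its visit interaction, non-inferiority is judged on that model, and the 337 per arm reproduces. Nor do they say that any non-significant interaction counts as support; the wording is limited to qualitative interactions.

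**What to change.** - In the HbA1c interaction and subgroup code, restore `BASE` and `BASE*AVISITN` so that it matches SAP 7.1.2.
- In SAP 7.1.1.2, add a test of `TRT01PN*BASE` with `TRT01PN*BASE*AVISITN`, and report the Week 26 slope difference with its confidence interval.
- Keep the <8% / ≥8% estimates, from a model that contains `BASE`, to show whether the effect changes direction.
- In the FPG-tertile model, add continuous baseline FPG and its interaction with visit.
- Record in SAP 2.1 any use of the category that departs from Protocol 8.3.3.1.

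The cost is a sentence or two of text and a few model terms. No new data are needed.
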